## Additional Adverse Events

The above incidences of each adverse event were reported from the Adaptive CRT study or published papers. Other events that have been experienced in other studies or have the potential to be experienced by subjects, but were not recorded in the Medtronic studies (or may have been reported with different terminology) also include:

Cardiac rupture, cardiac tamponade, depression, device battery issue, device rejection, dysplasia, electrical conduction disorders, emotional distress, implant tool delivery problem, tissue fibrosis, tissue necrosis, implant site seroma, inappropriate device therapy, inappropriate shocks, keloid scar, lead abrasion and discontinuity, insulation or conductor failure, mortality due to inability to deliver therapy, myocardial irritability or damage, nerve damage, pacemaker syndrome, pericardial rub, transient ischemic attack, valve damage, or venous stenosis.

## 18. Version History

Version	Summary of Changes	Author(s)/Title
1.0 28-MAR-2019	

Not Applicable, New Document

	[name], Clinical Research Specialist  [name], Principal Clinical Research Specialist  [name], Principal Clinical Research Specialist  [name], Senior Principal Statistician
2.0 29-DEC-2020	

CIP template transitioned from v A to v B;

Minor editorial updates;

Updated Lead Principal Investigator address;

Updated Table 1: Study sponsor contact information;

Removed "Cognizant Technology Solutions" as CRO from Table 2: CRO and Core Laboratory information;

Updated synopsis to reflect updates to the CIP;

Approximate number of centers increased from 55 to 60 in section 3.3;

Section 4.3 updated to include an additional ancillary objective to characterize reverse remodeling measured via echocardiography;

Section 5.1 language updated to accurately capture enrollment start and to extend study duration as necessary due to the unforeseen impact of COVID-19;

	[name], Clinical Research Specialist  [name], Clinical Research Manager  [name], Sr. Principal Statistician  [name], Sr. Clinical Research Specialist

	

• Section 6.6 updated to include CareLink SmartSync™ Device Manager as a Medtronic CareLink programmer;

• Section 6.7 updated to include MyCareLink Relay™ Home Communicator and MyCareLink Heart™ mobile app as suitable Medtronic CareLink home monitors;

• Section 7.3 updated to accept ECGs up to 50 days prior to enrollment;

• Section 8.2 updated to clarify that a Google Chrome and/or Safari are also suitable for data entry;

• Table 4 (Section 8.3) updated to include Echocardiography data collection;

• Sections 8.6 and 8.7 updated to clarify that baseline data should reflect pre-implant data when a patient is enrolled post-implant;

• Echocardiography data collection (only if standard of care) added to sections 8.6 (Baseline) and 8.9.1 (3, 6, and 12 month Follow-up visits);

• Section 8.8.1 updated to clarify that deviations from programming recommendations are not considered study deviations;

• Section 8.10 updated to include .pkg files as an acceptable device interrogation file;

• Row added to Table 9: Adverse Event classification responsibilities to capture sponsor responsibilities for death classifications;

• Section 13.1 updated to remove reference to ISO 14155:2011;

• Since a Mid-Q Response Publication Plan has been finalized, Appendix A was removed.

	
--	---	--

6.4	Handling of Missing, Unused, and Spurious Data and Dropouts	23
6.5	Adjustments for Multiple Comparisons	24
6.6	Interim Analyses.....	24
6.7	Subgroup Analyses	24
6.8	Changes to Planned Analysis	25
7.	Determination of Sample Size	25
8.	Validation Requirements.....	25
9.	References	25

1. Version History

Version	Summary of Changes	Author(s)/Title
1.0	Not Applicable, New Document	[REDACTED], Principal Statistician

2. List of Abbreviations and Definitions of Terms

Abbreviation	Definition
aCRT	Adaptive Cardiac Resynchronization Therapy, or AdaptivCRT®
AE	Adverse Event
AF	Atrial Fibrillation
Bi-V	Biventricular, e.g. both left and right ventricles
CIP	Clinical Investigation Plan
CCS	Clinical Composite Score
CRT	Cardiac Resynchronization Therapy
CV	Cardiovascular
ECG	Electrocardiogram
HF	Heart Failure
ITT	Intention-To-Treat
KCCQ	Kansas City Cardiomyopathy Questionnaire
LBBB	Left Bundle Branch Block
LOCF	Last Observation Carried Forward
LV	Left Ventricle; alternatively, Left Ventricular
LVEF	Left Ventricular Ejection Fraction
MAR	Missing At Random
MCAR	Missing Completely At Random
NMAR	Not Missing At Random
NYHA	New York Heart Association
SAP	Statistical Analysis Plan

3. Introduction

The purpose of the Statistical Analysis Plan (SAP) for the Mid-Q Response trial is to provide pre-analysis documentation and rationale for the statistical procedures that will be employed in the planned analyses that are performed throughout this study. Specifically, this plan outlines methods used in the study's final report. It does not limit the analysis that will be completed, as further analysis beyond what is specified in this document is likely.

This SAP was developed based on version 1 of the Mid-Q Response Clinical Investigation Plan (CIP), dated 28-MAR-2019. Topics addressed in this document but not the CIP include analysis methods for the ancillary objectives (sections 6.2.6 – 6.2.9), pooling methods (section 6.3), handling of missing data (section 6.4) and validation requirements (section 8). Details about randomization will be documented in the study-specific Randomization and Blinding Plan, but are considered out of scope for this SAP.

The objective of the Mid-Q Response study is to provide stronger evidence about the effectiveness of the AdaptivCRT® (aCRT) algorithm compared to standard CRT therapy in heart failure patients with moderate QRS duration (hence, in the **Middle of the QRS range**), left bundle branch block (LBBB) and preserved atrioventricular conduction. Currently, a limited evidence base from a few retrospective studies exists to support the hypotheses that patients in this subgroup who are of Asian ethnicity or of smaller body size may experience aCRT benefit. Thus, a demonstration of benefit from aCRT in this subpopulation may help to give additional heart failure patients access to a beneficial therapy, and, in addition, provide insights regarding guidelines for CRT in Asian countries.

4. Study Objectives

The listed objectives will test the hypothesis that the aCRT algorithm is superior to standard CRT therapy with regard to patient outcomes.

4.1 Primary Objective

The primary objective of the Mid-Q Response study is to test the hypothesis that aCRT ON increases the proportion of patients that improve on the Clinical Composite Score (CCS) compared to aCRT OFF at 6 months of follow-up.

The analysis will include all randomized patients and will follow the intent-to-treat principle. A secondary analysis will be done including only the patients for whom the echocardiogram (ECG) Core Laboratory confirmed the presence of LBBB and mid-range QRS.

4.2 Secondary Objectives

- To evaluate the change in New York Heart Association (NYHA) class at 6 and 12 months between the aCRT ON group and the aCRT OFF group.
- To characterize occurrence of hospitalizations for worsening heart failure in the aCRT ON group and the aCRT OFF group at 12 months.
- To characterize all-cause and cardiovascular related mortality in the aCRT ON group and the aCRT OFF group at 12 months.

4.3 Ancillary Objectives:

[figure not shown]
5. Investigation Plan

Medtronic Inc. and Medtronic Japan Co., Ltd. are sponsoring the Mid-Q Response study; a prospective, randomized, controlled, interventional, single-blinded, multi-center, post-market Cardiac Resynchronization Therapy in heart failure clinical study. The study is expected to be conducted at approximately 55 centers in Asia, including Japan, China, Taiwan, South Korea, Hong Kong, Malaysia, Singapore, Indonesia, Brunei, and the Philippines. Proposed study start is mid-2019.

The purpose of this study is to assess if CRT indicated patients with normal AV conduction, LBBB, and QRS ≥ 120 and < 150 ms treated with aCRT (aCRT ON: Adaptive Biventricular [Bi-V] and Left Ventricular [LV]), have a better Clinical Composite Score at 6 months than patients treated with standard BiV pacing (aCRT OFF: Nonadaptive CRT). To assess the superiority of CRT devices containing the aCRT algorithm, the primary objective of the Mid-Q Response study is to test the hypothesis that aCRT ON increases the proportion of patients that improve on the Clinical Composite Score (CCS) compared to aCRT OFF at 6 months of follow-up. Eligible subjects will be randomized after baseline assessment and implant of a CRT system containing the aCRT algorithm. Randomization will be done in a 1:1 ratio to either treatment (aCRT ON, Adaptive Bi-V and LV) or control (aCRT OFF, Nonadaptive CRT) groups. All subjects, independent of randomization assignment, will have a Medtronic CRT system. Study subjects will be followed for 12 months. A single analysis of objectives will be performed after all subjects have exited the study; no interim analyses are planned. See figure 1 below for a diagrammatic representation for these aspects. Further rationale for the study design can be found in the CIP.

A total of 220 randomized patients followed through 6 months are needed for the study's primary analysis. To achieve this, we anticipate enrolling 232 patients.

5.1 Figure 1: Study Flow

6. Statistical Methods

6.1 Study Subjects

6.1.1 Disposition of Subjects

Subjects will have their eligibility assessed at baseline. The final report will provide a listing of any subjects that fail to satisfy the study's entry criteria. In the final report, a diagram or figure will describe (at a minimum) the following:

- Number of eligible subjects who consented and enrolled
- Of consented and enrolled, number randomized to aCRT ON and number randomized to aCRT OFF
- Subjects withdrawing consent or withdrawn by investigator prior to therapy initiation
- Subjects with initiation of therapy.
- Subjects with LBBB confirmed on ECG by core lab

- Withdrawals, early exits, deaths and planned study exits (i.e. after the 12-month follow-up visit) that occur after treatment initiation.

For the final report, these will be described by randomized group wherever appropriate. For any study progress reports prepared prior to the final report, descriptions of withdrawals, early exits, deaths and other events occurring after randomization will be presented for both treatment groups in aggregate.

6.1.2 Clinical Investigation Plan (CIP) Deviations

Protocol deviations will be described using frequency tables and listings. Subjects will be excluded from analysis of the primary efficacy objective if the subject withdraws consent to be studied prior to randomization. Handling of visit window deviations as it affects the study's primary endpoint is discussed further in section 6.2.2.4.

6.1.3 Analysis Sets

The **Full Analysis Set** consists of all enrolled subjects who provide informed consent (as determined by local regulations for the enrolling site at the time consent is given). The Full Analysis Set will not be used for any pre-planned objectives; its principal uses are in enabling the reporting of adverse events that occur prior to randomization, and in describing subjects who initially consent, but do not go on to be randomized. It is further noted that no such analyses are currently planned and that these would be ad-hoc.

An Intention-to-Treat analysis will be performed and will serve as the primary basis for inference about all objectives in this study. **The Intention-to-Treat (ITT) Set will include all randomized subjects.** Per the ITT principle, subjects' will be considered as part of the "aCRT on" or "aCRT off" treatment groups solely by their assigned randomization, regardless of their adherence with the entry criteria, regardless of the treatment they actually received, and regardless of subsequent withdrawal from treatment or deviation from the protocol (Fisher 1990). For purposes of brevity, such an approach will be described using the shorthand of "ITT analysis" throughout this SAP. For example, "analysis for this endpoint will be ITT" means that (as described above) all randomized subjects will be included and analyzed according to random assignment, and the ITT dataset will be used.

Two objectives (the analysis of the primary endpoint and the ancillary objective of comparing KCCQ scores by treatment) will also feature sensitivity analyses that will be conducted in the subset of subjects treated 'per-protocol'. This cohort of randomized subjects is defined by all of the following:

- LBBB and QRS duration \geq 120 ms and $<$ 150 ms at the baseline ECG, as confirmed by the ECG Core Lab
- no documented inclusion or exclusion criteria violations at baseline
- no non-assigned aCRT programming between day 7 after randomization and the subject's 6-month visit
- no deviations for crossover between treatment groups

This grouping of subjects will be referred to as the **per-protocol** cohort.

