## 8.16. Deviation Handling

A study deviation is defined as an event within a study that did not occur according to the Clinical Investigation Plan or the Clinical Trial Agreement. Crossover is considered a deviation, but additional requirements apply, see section 5.4.

Prior approval by Medtronic is expected in situations where the investigator anticipates, contemplates, or makes a conscious decision to deviate. Prior approval is not required when a deviation is necessary to protect the safety, rights or well-being of a subject in an emergency or in unforeseen situations beyond the investigator's control (e.g. subject failure to attend scheduled follow-up visits, inadvertent loss of data due to computer malfunction, inability to perform required procedures due to subject illness).

For medically justifiable conditions which preempt a subject's ability to complete a study-required procedure, it may be permitted to report only one deviation which will apply to all visits going forward. This may also apply for other unforeseen situations (e.g. the subject permanently refuses to complete a study required procedure and the data will not contribute to the primary endpoint analysis). However, prior approval from Medtronic is required for such situations.

All study deviations must be reported to Medtronic regardless of whether medically justifiable, pre-approved by Medtronic, an inadvertent occurrence, or taken to protect the subject in an emergency. In the occurrence of a corrupted device interrogation file, Medtronic may request a deviation to document that a readable interrogation file is unavailable.

In the event the deviation involves a failure to obtain a subject's consent, or is made to protect the life or physical well-being of a subject in an emergency, the deviation must be reported to the Ethics Committee as well as Medtronic within five (5) working days, or according to local requirements. Reporting of all other study deviations should comply with Ethic Committee policies and/or local laws and deviations must be reported to Medtronic as soon as possible upon the center becoming aware of the deviation. Refer to section 15.2 and 15.3 for deviation reporting requirements and timeframes for reporting to Medtronic and/or regulatory bodies.

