6.2.2.1 Endpoint Definition

The primary endpoint for the study will be the Clinical Composite Score (CCS) at 6 months (Packer, 2001). The CCS classifies patients according their clinical status at 6 months post-randomization into categories Improved, Unchanged, and Worsened. A patient is classified Worsened in case of death, hospitalization for worsening heart failure, worsened NYHA class (using last observation carried forward), or worsened status on the Global Assessment Score. Also, patients that exit the study or cross over because of worsening heart failure are classified Worsened. A patient is classified Improved when not Worsened and there is an improvement in NYHA class or Global Assessment Score. Patients that are not Worsened or Improved are Unchanged including all patients with missing NYHA class and Global Assessment Score data who are not classified Worsened because of death, HF hospitalization, exit or crossover (see flowchart in Figure 2 below). The main analysis will look at the percentage of patients with Improved CCS.

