6.2.2.4 Analysis Methods

Subjects' CCS will be classified according to the algorithm described in Figure 2 and section 6.2.2.1. All subjects' 6-month visits will contribute to the 6-month CCS assessment regardless of when they occur relative to the protocol-defined windows (183 to 223 days from randomization). Non-missing values for dates of death, exit or crossover due to worsening heart failure, or a heart failure event that occur within the interval of 0 to 182 days post-randomization will necessarily lead to a CCS value of 'Worsened' and therefore a value of non-improvement for the primary outcome variable. To be

considered as endpoint events, crossovers and study exits must be indicated on the following respective crossover and exit CRF fields:

Was this an intentional crossover due to worsening heart failure NO YES

Was the exit due to worsening heart failure NO YES

NYHA and patient global assessment scores at 6 months will be used for subjects when available, and will be carried forward from the month 3 visit if this data is not available from the 6 month visit. For subjects having neither a 3-month or a 6-month classification, the baseline value will be carried forward (thus leading to a CCS of 'Unchanged' and a primary outcome value of non-improvement).

SAS code for the derivation of the CCS at 6 months, taken from the AdaptResponse study, is available under separate cover, shortened and with modifications made to reflect differing 6-month visit windows in Mid-Q Response.

The main analysis will use a Chi-square test comparing the binary proportion of subjects classified as improved (e.g., the proportion not worsened and not unchanged) between randomized arms. The null hypothesis will be rejected if the two-sided p-value is < 0.05. In the event this occurs, and the point estimate of the proportion improved in the aCRT ON group is higher compared to the aCRT OFF group, it will be concluded that aCRT ON causes a higher proportion of subjects classified as improved. The following SAS code provides an example of what may be used for this analysis:

```
proc freq data = analysis.PrimaryObj;
table aCRT_ITT*CCS_Improved/chisq nocol nopercents riskdiff;
run;
```

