6.2.2.8 Sensitivity Analysis 2: Per-protocol Analysis in Confirmed Cases of Mid-Q LBBB

A second sensitivity analysis will be performed to analyze the per-protocol effect of the treatment upon the CCS at 6 months, in the subset of subjects treated per-protocol (i.e., in the per-protocol cohort defined in section 6.1.3). This second sensitivity analysis will proceed in the same manner as the main (ITT) analysis of the primary endpoint, with a chi-square test being used for the comparison of interest. Example SAS code is as follows:

```
*** Primary objective - sensitivity analysis #2;
proc freq data = analysis.PrimaryObj;
where perProtocol = 1;
table aCRT_act*CCS_Improved/nocol nopercnt chisq;
run;
```

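### The per-protocol cohort for the 6-month CCS has no end date on its crossover criterion, so patients can be excluded for a crossover in months 6 to 12, after the endpoint is normally fixed (minor; supportive analysis only).

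*SAP*

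**What the plan says.** SAP 6.1.3 defines one per-protocol cohort by four criteria: core-laboratory confirmation of LBBB and QRS duration, no eligibility violation, and two criteria on treatment received. The first treatment criterion is bounded in time: "no non-assigned aCRT programming between day 7 after randomization and the subject's 6-month visit". The second is not: "no deviations for crossover between treatment groups".

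SAP 6.2.2.8 (Sensitivity Analysis 2) sets out to estimate the "per-protocol effect of the treatment upon the CCS at 6 months, in the subset of subjects treated per-protocol". It refers back to 6.1.3 for the cohort and adds no time limit. SAP 6.1.3 says the same cohort also serves a sensitivity analysis of the KCCQ.

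On crossover, Protocol 8.16 states: "Crossover is considered a deviation, but additional requirements apply, see section 5.4". Protocol 5.4 requires both a Crossover form and a Study Deviation form for a permanent crossover. Protocol 8.9.1 has crossovers reported as they occur at the 3, 6 and 12 month visits. SAP section 5 gives 12 months of follow-up and a single analysis after all subjects have exited.

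On the endpoint, SAP 6.2.2.1 states: "The primary endpoint for the study will be the Clinical Composite Score (CCS) at 6 months". SAP 6.2.2.4 counts a death, a heart failure event, or an exit or crossover due to worsening heart failure only when it falls "within the interval of 0 to 182 days post-randomization will necessarily lead to a CCS value of 'Worsened".

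**The concern.** A per-protocol analysis of a 6-month outcome should select patients on what happened up to 6 months. Here membership can also depend on what happened afterwards. A patient who kept the assigned programming through the 6-month visit, and whose score is settled, is removed if switched at month 8.

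The later switch may not be independent of the score. Investigators are not blinded (Protocol 12.1), and at the 6-month visit NYHA class and the patient global assessment are recorded. If a patient who has not improved is more likely to be switched afterwards, the exclusion removes non-improvers preferentially and raises the apparent Improved rate in the arm that loses them. If the two arms lose different numbers, the estimated treatment difference shifts. Even if late crossovers are unrelated to the score, valid on-treatment data are lost for no gain.

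**Working it through.** **Step 1. Can a late crossover enter the score?** Crossovers due to worsening heart failure count on days 0 to 182 (SAP 6.2.2.4). The 6-month window opens on day 183 (Protocol Table 6; SAP 6.2.2.4). A crossover after an in-window visit therefore falls on day 183 or later and cannot change the CCS. There is one exception. SAP 6.2.2.4 uses every 6-month visit whenever it occurs, so after a visit held before day 183 a crossover for worsening heart failure up to day 182 still makes the score Worsened.

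**Step 2. What does the crossover criterion add to the programming criterion?** A permanent crossover before the 6-month visit normally leaves non-assigned programming in place at some time between day 7 and that visit, so the programming criterion already excludes it. For permanent crossovers, the open-ended criterion therefore adds essentially those after the visit.

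**Step 3. Will late crossovers be in the data when the flag is built?** Yes. They are recorded as deviations through month 12, and the analysis follows all exits.

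**Step 4. Size.** The plan states no figure on this point to reproduce. Inputs:
- 220 randomized 1:1, so 110 per arm (SAP section 7). The actual cohort will be smaller, because the other criteria also remove patients.
- Improved 75% in aCRT ON and 55% in aCRT OFF (SAP section 7), that is 82.5 and 60.5 of 110.
- The number of late crossovers is an assumption. The 3% in SAP section 7 covers the first six months only. The same pace would give 0.03 × 110 = 3.3 per arm.

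If k non-improvers are dropped from an arm, its Improved rate becomes (number Improved)/(110 − k). The worst case for each arm is that every dropped patient is a non-improver:

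| Non-improvers dropped | Control rate | aCRT ON rate | Difference (points) | Shift (points) |
|---|---|---|---|---|
| None | 55.0% | 75.0% | 20.0 | 0 |
| 1, control only | 60.5/109 = 55.5% | 75.0% | 19.5 | −0.5 |
| 1, aCRT ON only | 55.0% | 82.5/109 = 75.7% | 20.7 | +0.7 |
| 3, control only | 60.5/107 = 56.5% | 75.0% | 18.5 | −1.5 |
| 3, aCRT ON only | 55.0% | 82.5/107 = 77.1% | 22.1 | +2.1 |
| 3 in each arm | 56.5% | 77.1% | 20.6 | +0.6 |

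With 3.3 in each arm the rates are 60.5/106.7 = 56.7% and 82.5/106.7 = 77.3%, again a difference of 20.6.

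**Step 5. Could the verdict of this analysis change?** Uncorrected Pearson chi-square, two-sided, with counts chosen near the threshold:
- 75/110 vs 60/110: p = 0.038. Dropping three non-improvers from each arm (75/107 vs 60/107): p = 0.034, no change. Dropping three from control only (75/110 vs 60/107): p = 0.066.
- 73/110 vs 60/110: p = 0.073. Dropping three from aCRT ON only (73/107 vs 60/110): p = 0.039.

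A change of verdict in these examples needs a result already near 0.05, losses in one arm only, and every lost patient a non-improver.

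**The case against.** The strongest reply is that little depends on this. Intention-to-treat is the basis for inference on all objectives (SAP 6.1.3), no decision rule uses Sensitivity Analysis 2, and deviations are tabulated and listed (SAP 6.1.2), so late crossovers would be visible. That stands, and it makes the point minor.

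Second, late crossovers may be few. Protocol 5.4 requires Steering Committee approval outside clinical or technical urgency and asks sites to keep the assignment for the whole study. The number could be zero, and then the shift is zero. That also stands.

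Third, a reader might infer that late crossovers follow from the 6-month result, and so will be mostly non-improvers, or that the treatment effect will be diluted by several points. The documents support neither. They do not say why late crossovers would occur, technical reasons are possible, and if the cause is unrelated to the score the expected bias is zero. A drop of several points requires all the losses to fall in the control arm; equal losses give about +0.6. What remains is that a relation is plausible and its direction unknown.

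Fourth, the open end may have been meant for the KCCQ, which Protocol 4.3 assesses at 6 and 12 months. The KCCQ section of the SAP is redacted, so the intention cannot be checked, and the wording should not be called a plain oversight. Even so, a 12-month use does not justify the rule for a 6-month score, and the programming criterion stops at 6 months in any case.

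Finally, an analyst might read the 6-month limit across from the neighbouring criterion. But that criterion states its limit and this one does not, so a flag programmed as written would have none.

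**Conclusion.** The point holds, at minor priority. As written, SAP 6.1.3 and 6.2.2.8 together exclude patients from a 6-month analysis for crossovers after the 6-month visit. After an in-window visit these cannot affect the CCS but may be related to it. The exclusion costs valid data and can bias the supportive per-protocol estimate in either direction.

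The size is an illustration, because it rests on an assumed number of late crossovers, on all of them being non-improvers, and on the full 110 per arm. On those terms the shift runs from zero with no late crossovers, through about +0.6 points with three per arm, to −1.5 or +2.1 points with three in one arm only. The primary result and the sample size of 220 randomized (232 enrolled) do not depend on this cohort.

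**What to change.** In SAP 6.1.3, for the CCS, restrict the crossover criterion to the period from randomization to the subject's 6-month visit, or to day 182 if that visit is earlier or missed. The day-182 limit covers the early-visit exception, because it is the last day on which a crossover for worsening heart failure can enter the score.

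For any 12-month use of the cohort, such as the KCCQ, define a separate flag that applies both the programming and the crossover criteria through the 12-month visit.

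The cost is one clause in the SAP, a date filter in the CCS flag and, if wanted, a second flag. Make the change before results by treatment group are seen.
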